| Safety and efficacy assessments: | 
Efficacy assessments:
 
Disease assessments [computerized tomography (CT) of the chest, abdomen, and pelvis or magnetic resonance imaging (MRI) of the abdomen and pelvis with a non-contrast CT scan of the chest in patients for whom CT scans with contrast are contraindicated] will be performed using RECIST v.1.1 every 9 weeks (\pm 7 days) from the first dose of study treatment up to one year (more frequently if clinically indicated). All subjects who remain on treatment for a year will subsequently have imaging performed every 12 weeks (\pm 7 days). Imaging should continue to be performed until radiologic evidence of disease progression, treatment discontinuation, the start of new anti-cancer treatment, withdrawal of consent, death, or the end of the study, whichever occurs first.
 
Bone scans will also be used to assess bone metastases. If a subject has a known history of bone metastases or has new bone pain during screening, a bone scan should be obtained prior to study entry. A bone scan at follow-up is required only if they develop new or worsening symptoms or if the site believes they have attained a complete response. If a subject has no known metastatic disease in the bone or active symptoms, a bone scan at baseline is not needed.
 
Brain imaging during the trial should be performed in subjects with known brain metastases (every nine weeks for first year, then every 12 weeks) and those with worsening and/or new neurological symptoms.
 
After disease progression by RECIST v.1.1, if the site Investigator determines the subject is clinically stable and will benefit from continued treatment, the subject will then be managed by irRECIST.
 
Each assessment will be performed as scheduled according to the calendar regardless of any dosing delay to prevent the introduction of bias into the assessment of efficacy. Failure to perform any of the
 |

| | |
|-----------|--|
| | 
required disease assessments will result in the inability to determine disease status for that time point.
 
Safety assessments:
 
The occurrence and maximum grade of adverse events (AEs) observed throughout the study will be listed. . Any AEs that the Investigator reports as unrelated to the drug will also be reported. In this study, AEs will be assessed according to the NCI CTCAE v.4.0.3.
 |

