6.4.3 OS and PFS definitions

OS is defined as the time from first dose of study treatment to death due to any cause. Subjects without documented death at the time of the final analysis will be censored at the date of the last follow-up.

PFS is defined as the time from first dose of study treatment to the first documented disease progression based on RECIST v.1.1 or death due to any cause, whichever occurs first.

6.4.4 irRECIST

Immunotherapeutic agents such as MK3475 (pembrolizumab) may induce antitumor effects by potentiating endogenous cancer-specific immune responses. The response patterns observed with these compounds may be different to the typical time course of responses seen with classical cytotoxic agents, and can manifest a clinical response after an initial increase in tumor burden or even the appearance of new lesions. Standard RECIST v.1.1 may, therefore, not provide a precise response assessment of immunotherapeutic agents such as MK3475 (pembrolizumab) .

irRECIST is RECIST v.1.1 adapted to account for the unique tumor response seen with immunotherapeutic agents. In this way, in subjects who have initial evidence of radiological disease progression by RECIST v.1.1, it is at the discretion of the Investigator whether to continue a subject on study treatment until repeat imaging is obtained. Subjects may receive study treatment and tumor assessment should be repeated at least four weeks later in order to confirm disease progression by irRECIST. Any subject deemed clinically unstable should be discontinued from trial treatment at first radiologic evidence of disease progression and is not required to have repeat imaging for disease progression confirmation. Clinical stability is defined as the following:

- Absence of symptoms and signs indicating clinically significant disease progression, including worsening of laboratory values.

- No decline in ECOG performance status.
- Absence of rapid progression of disease.
- Absence of progressive tumor at critical anatomical sites (e.g., cord compression) requiring urgent alternative medical intervention.

In determining whether or not the tumor burden has increased or decreased per irRECIST, the local site Investigator should consider all target and non-target lesions as well as any incremental new lesion(s). Scenarios where disease progression is confirmed at repeat imaging if any of the following occur by irRECIST:

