6.2.1 Summary statistics

Efficacy:

- CBR is defined as the number of subjects with complete response (CR), partial response (PR) or stable disease (SD) for at least 24 weeks based on RECIST v.1.1 divided by the number of patients in the analysis set (in subjects with PD-L1 positive tumors). Tumor response will be defined as best response. The CBR results will be presented as number and proportion of patients with clinical benefit and 95% CI of the proportion.
- The radiological PFS is defined as the time from the first dose of treatment until death by any cause or objective tumor progression according to RECIST v.1.1. Patients with

EudraCT number: 2016-004513-27

no progression or death will be censored at the date of their last evaluable imaging.

PFS censoring rules will follow FDA guidance in 2007 (see Table 1 - Appendix I).

- The first dose of treatment is defined as the minimum date of the first administration of eribulin and/or pembrolizumab.
- The PFS as assessed by investigator is defined as the time from the first dose of treatment until death by any cause or objective tumor progression as assessed by investigator according to RECIST v.1.1. Patients with no progression or death will be censored at the date of their last evaluable imaging. PFS censoring rules will follow FDA guidance in 2007 (see Table 2- Appendix I).
 - The first dose of treatment is defined as the minimum date of the first administration of eribulin and/or pembrolizumab.
- The OS is defined as the time from the first dose of treatment until death by any cause or the last date the patient was known to be alive. Patients who are lost to follow-up and the patients who are alive at the date of data cut-off will be censored at the date the patient was last known alive (censoring rules are specified in Table 3 - Appendix I).

A Kaplan-Meier survival analysis will be carried out to analyse PFS and OS. Number of events, median survival time and the corresponding 95% CI will be provided. Survival curves will be reported.

- The ORR is defined as the number of patients with CR and PR divided by the number of patients in the analysis population. Tumor response will be defined as best response, based on local investigator's assessment according to RECIST v.1.1. ORR will be reported as a proportion with the corresponding 95% CI.

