Appendix I

Table 1. Censoring rules for PFS

Situation	Date of progression or censoring	Outcome
Progression documented between scheduled visits	Earliest of: 
• Date of radiological assessment showing new lesion (if progression is based on new lesion); or• Date of last radiological assessment of measured lesions (if progression is based on increase in sum of measured lesions); Or	Progressed
Death before first progression disease assessment	Date of death	Progressed
Death between adequate assessment visits	Date of death	Progressed
No progression	Date of last radiological assessment of measured lesions	Censored
Treatment discontinuation for undocumented progression	Date of last radiological assessment of measured lesions	Censored
Treatment discontinuation for toxicity or other reason*	Date of last radiological assessment of measured lesions	Censored
Death or progression after more than one missed visit *	Date of last radiological assessment of measured lesions	Censored

* In accordance with these criteria death after the end of treatment visit will be considered as censored with the date of last radiological assessment of measured lesions.

Table 2. Censoring rules for PFS as assessed by investigator.

Situation	Date of progression or censoring	Outcome
No baseline assessment	Randomization + 1 day	Censored
Progression documented* between scheduled visits	Next scheduled visit	Progressed
No progression	Date of last visit with adequate assessment	Censored
Investigator's claim of progression*	Scheduled visit (or next scheduled visit if between visits)	Progressed
Treatment discontinuation for toxicity or other reason **	Date of last visit with adequate assessment	Censored
New anticancer treatment started with no claim of progression	Date of last visit with adequate assessment	Censored
Death before first progression disease assessment	Date of death	Progressed
Death between adequate assessment visits	Date of death	Progressed
Death after an extended lost-to-followup time (two or more missed assessments)**	Last visit with adequate assessment	Censored

* In addition to the progressions confirmed by radiological criteria, also the progressions evaluated by the investigator, without a radiological image confirming them, will be considered as PFS events.

** In accordance with these criteria death after the end of treatment visit will be considered as censored with the date of last adequate assessment.

Table 3. Censoring rules for OS

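### SAP investigator PFS dates between-visit progressions at the next scheduled visit and counts progressions without an image, against the protocol's definition and its own

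*SAP*

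**What the plan says.** - **Protocol 6.4.3** has one PFS, running from first dose to "the first documented disease progression based on RECIST v.1.1 or death due to any cause, whichever occurs first". Protocol 2.4 and SAP 4.2 list one RECIST v.1.1 PFS, plus the same endpoint in PD-L1 positive patients.
- **SAP 6.2.1** defines two PFS variables, a radiological one (Appendix I, Table 1) and one assessed by the investigator (Table 2). The event for the second is "death by any cause or objective tumor progression as assessed by investigator according to RECIST v.1.1". Both sets of rules are attributed to a 2007 FDA guidance, which is not reproduced and was not checked.
- **SAP Appendix I, Table 2** dates an investigator's claim of progression at "Scheduled visit (or next scheduled visit if between visits". A progression documented between visits also goes to the next scheduled visit. A death between adequate assessments keeps its own date. A footnote adds that "also the progressions evaluated by the investigator, without a radiological image confirming them, will be considered as PFS events".
- **SAP Appendix I, Table 1** handles "Progression documented between scheduled visits" by the date of a radiological assessment. It censors patients who stop treatment for undocumented progression. Its footnote censors deaths after the end of treatment visit at the last radiological assessment.
- **SAP 6.9** defines time to progression by the earlier of the progression date and death.
- **Protocol synopsis and 6.4.1** schedule scans every 9 weeks in the first year and every 12 weeks after that, "more frequently if clinically indicated" according to the synopsis.

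**The concern.** Moving events to scheduled dates can make assessment timing comparable between arms. This trial has one arm, so nothing is gained and an affected event simply receives a later date than the protocol gives it. Unscheduled scans follow clinical indication, so symptomatic progressions are the likely ones to be redated. The assigned visit may not even take place, because Protocol 3.1 and 6.4.1 end scheduled imaging at progression or treatment discontinuation. Table 2 also has a row anchored on randomisation, which this trial does not have, a sign that the table was not adapted to it.

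Two further matters are at stake. A variable described as objective RECIST progression would include events with no image. And the SAP has two PFS variables but never says in words which one is the protocol's secondary endpoint.

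**Working it through.** The documents give no figure for PFS timing, so there is none to reproduce. The stated design figure does reproduce: P(X ≥ 17 | n = 39, p = 0.30) = 0.04998, P(X ≥ 17 | n = 39, p = 0.50) = 0.832, and 39 / 0.9 = 43.3, rounded up to 44. It concerns CBR and does not use Table 2.

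**1. Direction of the dating rule.** Let a progression be documented or claimed at time t, with the next scheduled visit at v > t. The actual date is t and Table 2 gives v. The delay v − t is always positive, and no row moves a progression earlier.

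**2. Size per affected patient.** If events fall evenly over time (assumption), the mean delay is ΣL² / (2ΣL) for visit gaps of length L. Scan gaps come from Protocol 6.4.1, clinic gaps from Protocol 6.2 and Appendix 1 (days 1 and 8 of a 21-day cycle).

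| Reading of scheduled visit | Gaps (weeks) | Maximum | Mean |
|---|---|---|---|
| Scan, year 1 | 9 | 9 | 81/18 = 4.5 |
| Scan, later | 12 | 12 | 144/24 = 6.0 |
| Clinic visit | 1 and 2 | 2 | (1 + 4)/6 = 0.83 |

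A simulation of 400,000 patients in each of 16 scenarios gave mean delays of 4.96 to 4.99 weeks (scan) and 0.83 to 0.84 week (clinic). Its assumptions, none of them in the documents except the medians of 2.6 and 4.1 months (Protocol 1.3.2 and 1.3.3), are: exponential progression with those medians; exponential survival after progression with median 4 or 10 months; and 10%, 20%, 30% or 50% of progressions claimed between scans without an image.

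**3. Size over all patients.** Mean PFS moves by the affected share times the mean delay: 0.10 × 4.97 = 0.5 week to 0.50 × 4.97 = 2.5 weeks on the scan reading, and 0.10 × 0.84 = 0.08 week to 0.50 × 0.84 = 0.42 week on the clinic reading. On the scan reading the median was unchanged in 11 of 16 scenarios, because events cluster at the week 18 scan. The largest change was from 13.5 to 18.0 weeks, or 4.5 weeks.

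**4. Progression followed by death before the next visit.** Take progression on an unscheduled scan at week 12 and death at week 15, with the next scan at week 18.
- Protocol 6.4.3 gives 12 weeks.
- Table 2, progression row, gives 18 weeks on the scan reading.
- Table 2, death row, gives 15 weeks.
- SAP 6.9 gives 15 weeks if the progression date is the Table 2 date, and 12 if it is the actual date.
- OS is 15 weeks.

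No rule of precedence chooses between these. To see how often the question arises, use P(death before next visit) = 1 − (1 − e^(−λL)) / (λL), with λ = ln 2 / (4.345 m) per week and m the median survival after progression in months:
- L = 9: 0.160 (m = 4), 0.096 (m = 7), 0.068 (m = 10).
- L = 12: 0.205, 0.125, 0.090.
- L = 2: 0.039, 0.022, 0.016.

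The simulation, with its mix of gaps, gave about 7% to 18% of affected patients on the scan reading. That is 0.3 to 3.9 of 44 patients (for example 44 × 0.50 × 0.175 = 3.9). On the clinic reading it is about 1% to 4% of affected patients.

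**5. Definition against footnote.** SAP 6.2.1 requires "objective tumor progression as assessed by investigator according to RECIST v.1.1". The footnote admits events with no image. Both describe the same variable, and they cannot both hold.

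**6. Net direction against Table 1.** Next-visit dating makes Table 2 later for progressions that have an image. Counting no-image progressions makes it earlier, because Table 1 censors them. In the simulation, where the between-scan events were of the no-image kind, the Table 2 median equalled the Table 1 median in 6 scenarios and was shorter in 10 (for example 18 against 27 weeks at a 4.1-month median with 20% affected). With more unscheduled scans the balance could go the other way.

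**The case against.** The case on the other side is substantial.

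- **Which PFS is the endpoint.** The SAP's list of tables and figures labels one PFS as according to RECIST v1.1 criteria and the other as according to investigator criteria, and Table 1 is captioned simply as the PFS rules. A reader might infer that either result could be passed off as the secondary endpoint. The labels make that less likely. What stands is that no sentence names the endpoint, and both versions receive the same subgroup tables and Kaplan-Meier curves.
- **PFS longer than OS.** A reader might infer that the plan lets PFS exceed survival. The death row of Table 2 and the earlier-of rule in SAP 6.9 can be read to cap it. What stands is the missing precedence rule.
- **Size.** If a scheduled visit is a clinic visit, the shift is under a week on average. That is a fair reading. The SAP leaves the term undefined.
- **Bias against earlier eribulin trials.** A reader might infer that the result is flattered against the medians cited in the protocol. The documents do not say how those trials dated between-visit progressions, so this cannot be shown.
- **Importance.** PFS is a secondary estimate in one arm, with no PFS hypothesis or threshold. That stands in full.

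**Conclusion.** The point holds as an inconsistency in the SAP. The Table 2 dating rule departs from Protocol 6.4.3 and can only delay an affected event. The delay is up to 9 weeks in year 1 and 12 later (mean about 4.5 to 5 weeks) if visits are scans, and about 0.8 week (maximum about 2) if they are clinic visits. The means assume events spread evenly between visits or the simulated progression pattern. The share of patients affected is unknown, so 10% to 50% is an assumed range. The conflict between the no-image footnote and SAP 6.2.1, and the absence of a precedence rule for death after progression, follow from the text and need no assumption.

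A reader might go further and conclude that investigator PFS is lengthened overall. The documents do not support that, because the dating rule and the no-image rule pull in opposite directions. A radiological RECIST PFS is still planned, and the 17-of-39 CBR decision is untouched.

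**What to change.** 1. In SAP Appendix I, Table 2, date progression on the day it was documented or claimed, never later than death.
2. State in SAP 6.2.1 that the radiological RECIST v.1.1 PFS under Table 1 is the protocol's secondary endpoint.
3. Label the Table 2 variable a sensitivity analysis that includes clinical progression, and remove the objective and RECIST v.1.1 wording from its definition.
4. Because Table 1 then carries the protocol endpoint, reconcile its footnote censoring deaths after the end of treatment visit with Protocol 6.4.3, which counts death from any cause.

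The cost is SAP wording only, with no new data. Reported investigator PFS may become slightly shorter. The changes should be made before the analysis, so that the choice between two PFS estimates cannot depend on the results.
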